5.3. Study Design Rationale

The purpose of Part 1 (dose escalation) is to identify a TRC253 dose and regimen that can be safely administered to patients with advanced cancer. The purpose of Part 2 (dose expansion) is to further characterize the safety, PK, and PD of the recommended dose as well as to explore clinical activity. In addition, the clinical activity of TRC253 in patients with metastatic CRPC whose tumors harbor an acquired resistance to enzalutamide or apalutamide driven by the AR F877L mutation (Cohort 1), a yet unknown mechanism sensitive to TRC253 treatment (Cohort 2), or the sole AR L702H mutation (Cohort 3) will be explored.

5.4. Starting Dose Rationale

The TRC253 starting dose for this study is 40 mg once daily in the morning. This TRC253 starting dose is less than the safe starting dose according to Food and Drug Administration (FDA) guidelines for oncology agents in cancer patients, using nonclinical safety data.

The selection of the TRC253 starting dose is supported by toxicology results obtained in the rat as the most sensitive species. In the rat, the severely toxic TRC253 dose in 10% of the rats (STD10) was determined to be 100 mg/kg. The human equivalent dose (HED) was calculated by normalization of the TRC253 dose to the body surface area. A default safety factor of 10 was applied to provide a margin of safety for protection of human patients relative to STD10 and a TRC253 dose of 60 mg/m² was determined. In consequence, for a human with a surface area of 1.8 m², the highest potential starting dose was calculated to be 108 mg.

However, the final selection of the starting dose was ultimately based on the potential pharmacologic activity of TRC253. Pharmacologic efficacy parameters were obtained from the LNCaP F877L mouse xenograft model and the Hershberger assay that assessed the effect of TRC253 on androgen dependent organ development) to estimate the potential efficacious TRC253 concentration and plasma exposure in humans. Applying these parameters, a TRC253 starting dose of 65 mg once daily was projected to achieve the median target human exposure (335 ng/mL) over the 24 hr dosing interval. A dose of 40 mg per day was therefore selected to provide for a starting dose expected to be safe without causing complete AR receptor occupancy.

6. INVESTIGATIONAL PLAN

6.1. Study Procedures

6.1.1. Trial Overview

The study is divided into 3-4 periods: a Pre-Screening Period (Part 2 only), a Screening Period, a Treatment Period, and an End of Treatment/Follow-up Period. The Schedules of Assessments (Table 7 and Table 8) summarize the frequency and timing of efficacy, PK, PD, biomarker, and safety measurements applicable to this study.

Adverse events and concomitant therapies will be recorded from signing of informed consent through 28 days post dose or patient's participation in the study if the last scheduled visit occurs at a later time. Follow-up toxicity assessments will be obtained monthly until study treatment-related toxicities have resolved (baseline or \leq Grade 1) or are deemed irreversible.

6.1.2. Pre-Screening Period (Part 2 Only)

Blood samples will be collected and screened for LBD mutations of the AR using a ctDNA based assay. Up to 15 patients whose blood samples test positive for the AR F877L mutation will be enrolled into Cohort 1. Up to 30 patients without the AR F877L and without sole AR L702H mutations will be enrolled into Cohort 2. Up to 15 patients whose blood samples test positive for the sole AR L702H mutation will be enrolled into Cohort 3. Note that Cohort 1 patients may be positive for F877L alone or associated with any other AR mutation.

Potential patients must sign the separate ICF authorizing the collection, transfer, storage, and processing of the AR mutation sample(s) for genetic research. Consent must be obtained prior to collection of the first AR mutation sample. Participation in this genetic research is required for participation in the study. The status of the F877L and L702H mutations must be reported on the enrollment checklist in order to confirm eligibility and assignment to Cohort 1, 2, or 3.

6.1.3. Screening Period

Parts 1 and 2:

All patients must sign the main ICF prior to the conduct of any study-related procedures. Screening procedures will be performed up to 28 days before the first dose of drug.

During the Screening Period, medical history and eligibility criteria will be reviewed and a complete clinical evaluation will be performed, which includes a physical examination, vital signs measurements, physical measurements, and ECG. A brain MRI (or if contraindicated, CT) scan will be performed to determine eligibility.

Laboratory tests (performed at the local laboratory) noted in the inclusion criteria (Section 7.2) must be within the limits specified in the inclusion criteria prior to the start of dosing.

Prior therapies will be recorded.

6.1.4. Treatment Period

Laboratory tests do not need to be repeated at cycle 1 day 1 if they were completed within 7 days prior in screening.

Part 1 Cycle 1

Patients will receive a single dose of TRC253 on Cycle 1 Day 1 for PK studies. No food should be consumed for at least 8 hours before and 4 hours after the TRC253 dosing. Blood pressure and heart rate will be measured prior to dose administration and hourly (± 15 minutes) for the first 6 hours following the first dose of study drug administration on Cycle 1 Day 1.

To aid in selection of the RP2D, patients may undergo PET scans using FDHT, a radiopharmaceutical specifically designed to image binding to AR. In these patients, FDHT-PET scans will be obtained before initiation of therapy. Imaging will occur at 1 or more centers under their existing IND and institutional protocol.

Safety, PD, biomarker, and disease evaluations will be performed as specified in the Time and Events Schedule for Part 1 ([Table 7](#)).

Treatment Cycles

TRC253 capsules will be self-administered once daily in the morning from Cycle 1 Day 1 onwards (Cycle 2 Day 1 onwards for Part 1). On extended PK days, no food should be consumed for at least 8 hours before and 4 hours after the TRC253 dosing. On all other days, no food should be consumed for at least 2 hours before and 1 hour after dosing.

Safety, PK, PD, biomarker, and disease evaluations will be performed at the time points specified in the Schedules of Assessments ([Table 7](#) and [Table 8](#)).

Treatment will continue until one or more of the withdrawal criterion are met (refer to [Section 7.4.3](#)).

Part 1: Once the first expansion cohort reaches its primary endpoint, patients from the dose escalation phase of the study who continue to derive benefit from TRC253 treatment will be allowed to stay on treatment and will attend monthly visits, which are to occur a minimum of once every 4 weeks (± 2 days).

Part 2: Once the primary endpoint is reached in the expansion cohort, patients who continue to derive benefit from TRC253 treatment will be allowed to stay on treatment and will attend monthly visits, which are to occur a minimum of once every 4 weeks (± 2 days).

Study procedures to be performed at the monthly visits are specified in the Schedules of Assessments ([Table 8](#)).

6.1.5. End of Treatment and Follow-Up Period

The End of Treatment visit will be 7 days (± 2 days) after the last dose of TRC253.

The Follow-Up visit will be 28 days (± 7 days) after the End of Treatment visit. Study procedures to be performed at the follow-up visit are specified in the Schedules of Assessments ([Table 7](#) and [Table 8](#)). Patients who have unresolved study-related toxicities will have extended

follow-up once monthly until study treatment-related toxicities have resolved (baseline or \leq Grade 1) or are deemed irreversible.

Table 7: Part 1 Dose Escalation Schedule of Assessments

Study Procedures	Notes	Screening	Cycle 1 (7 days)		Cycle 2 (28 days)				Cycles 3+ (28 days)	End of Treatment	Follow-Up (EOT+28 days)
		Day -28	Day 1	Day 4	Day 1	Day 8	Day 15	Day 22	Day 1		
Screening/Administrative											
Sign main informed consent form	Informed consent must be obtained before any study-related procedures.	X									
Inclusion and exclusion criteria		X									
Brain MRI	To determine eligibility. If MRI is clinically contraindicated, a brain CT will be performed.	X									
Medical history and demographics		X									
Prior therapies		X									
Study Drug Administration											
Study Drug Administration	On extended PK days, no food should be consumed for at least 8 hr before and 4 hr after TRC253 dosing. On all other days, no food should be consumed for at least 2 hrs before and 1 hr after dosing. Patients will dose in the clinic on all PK days. Patients will track meal times on their home dosing logs.		X		Continuous daily administration from Cycle 2 Day 1 until one or more withdrawal criterion is met (see Section 7.4.3).						
Safety Assessments											
Physical examination	Full physical at screening, and targeted physical based on adverse events at subsequent visits. ECOG at screening.	X	X	X	X	X	X	X	X	X	X
Vital signs	BP, heart rate, respiration, and body temperature. In addition, on cycle 1 day 1, blood pressure and heart rate will be measured prior to dose administration and hourly (±15 minutes) for the	X	X	X	X	X	X	X	X	X	X

Study Procedures	Notes	Screening	Cycle 1 (7 days)		Cycle 2 (28 days)				Cycles 3+ (28 days)	End of Treatment	Follow-Up (EOT+28 days)
		Day -28	Day 1	Day 4	Day 1	Day 8	Day 15	Day 22	Day 1		
	first 6 hours following the first dose.										
Physical measurements	Height and weight at screening. Weight only is taken prior to each cycle and at EOT visit.	X			X				X	X	X
Hematology	Hemoglobin, RBC count, platelet count, WBC count with differential and absolute neutrophil count.	X	X		X		X		X	X	(X)
Coagulation	PT, aPTT, INR, and fibrinogen.	X			X				X	X	(X)
Serum chemistry	Serum chemistry parameters are listed in Section 12.1.2 . In addition, direct bilirubin is evaluated at screening if total bilirubin is > 1.5 ULN. Iron studies (serum iron, ferritin, and total iron binding capacity).	X	X		X		X		X	X	(X)
Fasting lipid panel	Total cholesterol, HDL cholesterol, LDL cholesterol, and triglycerides.	X							X (Every 3 cycles: C3, C6, etc.)	X	
TSH		X							X (Every 3 cycles: C3, C6, etc.)	X	
Urinalysis	Urinalysis parameters are listed in Section 12.1.2 . If dipstick result is abnormal, microscopy will be used to evaluate sediment.	X	X		X				X	X	
12-lead ECG	12-lead ECGs will be performed in triplicate (approximately 2 minutes between recordings) pre-dose at all visits indicated. In addition, ECGs will be performed predose, and 2, 4,	X	X		X	X	X	X	X	X	X

Study Procedures	Notes	Screening	Cycle 1 (7 days)		Cycle 2 (28 days)				Cycles 3+ (28 days)	End of Treatment	Follow-Up (EOT+28 days)
		Day -28	Day 1	Day 4	Day 1	Day 8	Day 15	Day 22	Day 1		
	and 8 hrs postdose (\pm 15 min) on Cycle 1 Day 1 and Cycle 3 Day 1. Refer to Section 8.5.3 for management of QTcF prolongation.										
Pharmacokinetics and Pharmacodynamics											
Blood pharmacokinetic sampling	Pharmacokinetic plasma samples will be obtained Cycle 1 as follows: 0 (pre-dose), 0.5, 1, 1.5, 2, 3, 4, 6, 8 hr (\pm 15 min), and 24 hr (\pm 1 hr), 72 hr (Day 4), and 168 hr (pre-dose on Cycle 2 Day 1); and on Cycle 3 Day 1 as follows: 0 (pre-dose), 0.5, 1, 1.5, 2, 3, 4, 6, 8 hr (\pm 15 min). Additional PK after inpatient dose escalation may be performed if deemed appropriate.		X (Extended PK 24 hrs)	X (Trough)	X (Trough)	X (Trough)	X (Trough)	X (Trough)	X (Extended PK 8 hrs, C3 only) Then, trough on even cycles	X (Trough)	X (Trough)
FDHT-PET	Imaging to determine receptor occupancy will be assessed in select patients. Only to be completed at select institutions.	(X) (within 7 days of CID1)							(X) (Cycle 3 only)		
Biomarkers											
AR mutation testing	See lab manual for further instructions.	X							X (Cycle 5 only)	X	
CTC collection	Enumeration and molecular profiling. See lab manual for further instructions.		X						X (Every 3 cycles: C5, C8, etc.)	X	
Testosterone, free testosterone, DHT, estradiol, DHEA-S,	The appropriate amount of serum should be drawn to be analyzed locally.	X (Testosterone only)	X						X (Every 3 cycles: C5, C8, etc.)	X	

Study Procedures	Notes	Screening	Cycle 1 (7 days)		Cycle 2 (28 days)				Cycles 3+ (28 days)	End of Treatment	Follow-Up (EOT+28 days)
		Day -28	Day 1	Day 4	Day 1	Day 8	Day 15	Day 22	Day 1		
androstenedione, and SHBG											
Archival Tumor Tissue	If available	(X)									
Disease evaluations											
Serum PSA		X	X		X				X	X	
CT or MRI scan of the chest and abdomen/pelvis	EOT assessments do not need to be repeated if they were performed within 28 days while on treatment.	X							X (C4, then every 3 cycles: C7, C10, etc.)	X	
Radionuclide bone scan		X							X (C4, then every 3 cycles: C7, C10, etc.)	X	
Ongoing review											
Concomitant therapy	Continuous from signing of informed consent through 28 days after EOT visit.										
Toxicity assessment/adverse events											

The allowable window for each visit within the cycle is ± 2 days unless otherwise stated.

The allowable window for FDHT-PET, Follow-Up visit, and all scans is ± 7 days.

(X) for an assessment at the Follow-Up (EOT+28 days) visit indicates the assessment does not need to be performed if there were no abnormalities observed for the assessment at the End of Treatment visit.

Safety assessments (except for ECG) on C1D1 do not need to be repeated if they were completed within 7 days prior in screening.

Table 8: Part 2 Dose Expansion Schedule of Assessments

Study Procedures	Notes	Pre-Screening	Screening	Cycle 1 (28 days)				Cycles 2+ (28 days)	End of Treatment	Follow-Up (EOT+28 days)
			Day -28	Day 1	Day 8	Day 15	Day 22	Day 1		
Screening/Administrative										
Sign genetic research informed consent form	Informed consent for the AR mutation sample must be obtained prior to collecting the sample.	X								
Sign main informed consent form	Informed consent must be obtained before any study-related procedures.		X							
Inclusion and exclusion criteria			X							
Brain MRI	To determine eligibility. If MRI is clinically contraindicated, a brain CT will be performed.		X							
Medical history and demographics			X							
Prior therapies			X							
Study Drug Administration										
Study Drug Administration	For all dosing days, no food should be consumed for at least 2 hrs before and 1 hr after dosing. Patients will dose in the clinic on all PK days. Patients will track meal times on their home dosing logs.			Continuous daily administration from Cycle 1 Day 1 until one or more withdrawal criterion is met (see Section 7.4.3).						
Safety Assessments										
Physical examination	Full physical at screening, and targeted physical based on adverse events at subsequent visits. ECOG at screening.		X	X	X	X	X	X	X	X
Vital signs	BP, heart rate, respiration, and body temperature. In addition, on cycle 1 day 1, blood pressure and heart rate will be measured prior to dose administration and		X	X	X	X	X	X	X	X

Study Procedures	Notes	Pre-Screening	Screening	Cycle 1 (28 days)				Cycles 2+ (28 days)	End of Treatment	Follow-Up (EOT+28 days)
			Day -28	Day 1	Day 8	Day 15	Day 22	Day 1		
	hourly (± 15 minutes) for the first 6 hours following the first dose.									
Physical measurements	Height and weight at screening. Weight only is taken prior to each cycle and at EOT visit.		X	X				X	X	X
Hematology	Hemoglobin, RBC count, platelet count, WBC count with differential and absolute neutrophil count.		X	X		X		X	X	(X)
Coagulation	PT, aPTT, INR, and fibrinogen.		X	X				X	X	(X)
Serum chemistry	Serum chemistry parameters are listed in Section 12.1.2 . In addition, direct bilirubin is evaluated at screening if total bilirubin is > 1.5 ULN. Iron studies (serum iron, ferritin, and total iron binding capacity).		X	X		X		X	X	(X)
Fasting lipid panel	Total cholesterol, HDL cholesterol, LDL cholesterol, and triglycerides.		X					X (Every 3 cycles: C3, C6, etc.)	X	
TSH			X					X (Every 3 cycles: C3, C6, etc.)	X	
Urinalysis	Urinalysis parameters are listed in Section 12.1.2 . If dipstick result is abnormal, microscopy will be used to evaluate sediment.		X	X				X	X	
12-lead ECG	12-lead ECGs will be performed in triplicate (approximately 2 minutes between recordings) pre-dose at all visits indicated. On cycle 1 day 15, ECGs in triplicate will be completed pre-dose and 6 hours post-		X	X	X	X (Pre-dose and 6 hours post-dose)	X	X	X	X

Study Procedures	Notes	Pre-Screening	Screening	Cycle 1 (28 days)				Cycles 2+ (28 days)	End of Treatment	Follow-Up (EOT+28 days)
			Day -28	Day 1	Day 8	Day 15	Day 22	Day 1		
	dose (+/- 15 min). Refer to Section 8.5.3 for management of QTcF prolongation.									
Pharmacokinetics and Pharmacodynamics										
Blood pharmacokinetic sampling	Plasma samples will be obtained pre-dose. On cycle 1 day 15, samples will be obtained pre-dose and 6 hours post-dose (+/- 15 min).			X	X	X (Pre-dose and 6 hours post-dose)	X	X	X	X
Biomarkers										
AR mutation testing	See lab manual for further instructions.	X						X (Cycle 5 only)	X	
CTC collection	Enumeration and molecular profiling. See lab manual for further instructions.			X				X (Every 3 cycles: C4, C7, etc.)	X	
Testosterone, free testosterone, DHT, estradiol, DHEA-S, androstenedione, and SHBG	The appropriate amount of serum should be drawn to be analyzed locally.		X (Testosterone only)	X				X (Every 3 cycles: C4, C7, etc.)	X	
Archival Tumor Tissue	If available		(X)							
Disease evaluations										
Serum PSA			X	X				X	X	
CT or MRI scan of the chest and abdomen/pelvis	EOT assessments do not need to be repeated if they were performed within 28 days while on treatment.		X					X (C3, then every 3 cycles: C6, C9, etc.)	X	
Radionuclide bone scan			X					X (C3, then every 3	X	

Study Procedures	Notes	Pre-Screening	Screening	Cycle 1 (28 days)				Cycles 2+ (28 days)	End of Treatment	Follow-Up (EOT+28 days)
			Day -28	Day 1	Day 8	Day 15	Day 22	Day 1		
								cycles: C6, C9, etc.)		
Ongoing review										
Concomitant therapy		Continuous from signing of informed consent through 28 days after EOT visit.								
Toxicity assessment/adverse events										

The allowable window for each visit within the cycle is ± 2 days unless otherwise stated.

The allowable window for Follow-Up visit and all scans is ± 7 days.

(X) for an assessment at the Follow-Up (EOT+28 days) visit indicates the assessment does not need to be performed if there were no abnormalities observed for the assessment at the End of Treatment visit.

Safety assessments (except for ECG) on C1D1 do not need to be repeated if they were completed within 7 days prior in screening.

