2.2.3. Pharmacokinetics and Product Metabolism in Animals

In male animals (mouse, rat, dog, and monkey), TRC253 is a low clearance molecule with a large volume of distribution (6-20 L/kg) and high oral bioavailability (79% to 91% except in mouse). The apparent elimination half-life (t_{1/2}) after an oral dose was longer in the dog and monkey (58 and approximately 50 hours) than in the mouse and rat (approximately 6 and 8 hours). *In vitro* plasma protein binding of TRC253 (1 to 20 μg/mL) was concentration dependent and generally similar for male animals and male humans, with the % free fraction ranging from 9.2% to 18.3% and 13% to 15.4%, respectively. Consistent with the large volume of distribution, extensive tissue distribution was observed in rats.

After repeated oral administration, absorption was moderate to slow in the male rat and dog dosed for up to 28 days (time of maximum observed plasma concentration [t_{max}] generally 2 to 7 hours), in tumor-bearing castrated mice dosed for 8 days (t_{max} 4 hours), and in castrated rats dosed for 10 days (t_{max} 3 to 14 hours). The dose-exposure relationship was generally nonlinear and there was evidence of accumulation in the rat and dog.

Limited metabolism was observed in human liver microsomes and hepatocytes (human, rat, and dog) *in vitro*. Although TRC253 is not highly metabolized, flavin-containing monooxygenases 1 and 3 and CYP3A4 are shown to be involved in the metabolism of the compound.

In vivo metabolism of TRC253 was studied in the male rat after a single oral administration of ¹⁴C-TRC253. Consistent with *in vitro* data, limited *in vivo* metabolism was observed with at least

80% of unchanged drug recovered in the urine and feces. M5, a pharmacologically inactive phenolic metabolite formed by oxidative dealkylation, was predominant in plasma (9.8% of the total drug related radioactivity) and was also present at low levels in urine and feces. After oral dosing, 92.9% of the radioactive dose was recovered in urine (17.7%) and feces (75.2%) within 96 hours post-dose. Fecal-biliary excretion of unchanged drug appears to be the major elimination pathway in the male rat.

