14.1. Analysis Populations

The analysis populations are as follows:

- **Safety population:** This population includes all patients who received at least 1 dose of study drug.
- **DLT evaluable analysis set:** This set is a subset of the safety population. Patients who receive $\geq 75\%$ of planned doses of TRC253 or who had a DLT during the DLT evaluation period will be included in this analysis.
- **PK analysis set:** This set consists of all patients who receive at least 1 dose of study drug and have at least 1 post dose concentration measurement of TRC253. This group will be used for summaries (tables and listings) and listings of derived PK parameters. Note: patients will be removed from the estimation of certain PK parameters on an individual basis due to, for example, missing PK samples such that the PK parameters cannot be appropriately derived. These patients will be identified at the time of the analyses along with their reason for removal.
- **Efficacy analysis set:** This population includes all patients who received at least 1 dose of study drug and underwent a relevant efficacy assessment.

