14.3. Endpoint Definitions

PSA Response at Week 12

PSA response is defined as a $\geq 50\%$ decline from baseline according to PCWG3 criteria ([Appendix 2](#)). An additional PSA obtained at least 4 weeks later must show $\geq 50\%$ decline from baseline to confirm the response.

Time to PSA Progression

Time to PSA progression is measured from the start of treatment until the criteria for PSA progression according to the PCWG3 are met ([Appendix 2](#)). Patient without PSA progression will be censored at the last PSA assessment.

Radiographic Progression-Free Survival (rPFS)

Radiographic Progression-Free Survival (rPFS) is measured from the start of the treatment until the criteria for radiographic disease progression are met or death occurs, whichever is first. Patient will be censored at the last disease assessment when no rPFS event is observed.

Pharmacokinetic Parameters

Pharmacokinetic parameters of TRC253 will be derived from plasma concentration versus time data after single dose and repeat dose, as applicable. The pharmacokinetic parameters to be assessed are shown below. Other parameters may also be assessed.

C_{max}	Maximum observed plasma concentration for each patient
C_{min}	Observed plasma concentration at the end of dosing interval for each patient
t_{max}	Time of maximum observed plasma concentration
AUC_{τ}	Area under the plasma concentration-time curve from time zero to 24 hours (dosing interval) at steady state
AUC_{last}	Area under the plasma concentration-time curve from time zero to the last time measured
AUC_{∞}	Area under the plasma concentration-time curve from time zero extrapolated to infinite time calculated as $AUC_{last} + C_{last}/\lambda_z$, where C_{last} is the last observed measurable (non-BQL) concentration; extrapolations of more than 20.00% of the total AUC are reported as approximations
λ_z	Apparent terminal elimination rate constant, determined by linear regression using the terminal log-linear phase of the log transformed concentration vs. time curve
$t_{1/2term}$	Apparent terminal elimination rate constant, determined by linear regression using the terminal log-linear phase of the log transformed concentration vs. time curve

$t_{1/2\text{eff}}$	Effective half-life
R_A	Accumulation Index
CL/F	Total apparent oral clearance
V_{ss}/F	Apparent oral volume of distribution at steady state

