The following requirements should be met for an acceptable calculation of $t_{1/2\text{term}}$, λ_z , AUC_∞ , and related parameters:

- A) at least 3 data points are used in the calculation, otherwise $t_{1/2\text{term}}$, λ_z , AUC_∞ , and related parameters are not assessable;
- B) coefficient of determination (r^2_{adj}) is at least 0.90.

If requirement (B) is not met, $t_{1/2\text{term}}$, λ_z , AUC_∞ , and related parameters will be reported as approximations.

Actual sampling times will be checked for major aberrations. In case a major aberration occurs for an actual sampling time of >20% deviation from the scheduled time (relative to study drug intake), this plasma concentration will be excluded from descriptive statistics in the plasma concentration table.

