14.5. Pharmacokinetic Analyses

All plasma concentrations below the lowest quantifiable concentration or missing data will be labeled as such in the concentration data presentations or SAS dataset. Concentrations below the lower quantifiable concentration will be treated as zero in the summary statistics. All patients and samples excluded from the analysis will be clearly documented in the Clinical Study Report.

Data will be listed for all patients with available plasma concentrations per dose level/Part. Patients will be excluded from the PK analysis if their data do not allow for accurate assessment of the PK (e.g., incomplete administration of the study drug; missing information of dosing and sampling times; concentration data not sufficient for PK parameter calculation).

Descriptive statistics will be used to summarize TRC253 plasma concentrations at each sampling time point, by dose level/study part. Pharmacokinetic parameters of TRC253 will be determined using non-compartmental analysis and summarized by dose level/study part. Mean and individual plasma TRC253 concentration time profiles will be plotted (linear and semilog) after the first dose of study drug and at steady state. Analysis of dose proportionality and steady state versus Day 1 accumulation ratios will be conducted.

A snapshot date for PK samples to be analyzed may be defined, if required. Samples collected before this date will be analyzed for TRC253 and included in the PK analysis. Samples collected after the snapshot date may be analyzed at a later date, and may be included in a PK re-analysis when they become available after database lock.

Population PK analysis of plasma concentration-time data of TRC253 will be performed using nonlinear mixed-effects modeling. Available baseline patient characteristics (demographics, laboratory variables, race, etc.) will be tested as potential covariates affecting PK parameters. Data from this study may be pooled with other data for the population analysis. Details will be given in a population PK analysis plan and the results of the population PK analysis will be presented in a separate report.

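### Does the 8-hour steady-state profile, with sparse Part 2 sampling, leave the 24-hour AUC and the other PK parameters without a usable analysis?

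*Combined protocol and SAP*

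**What the plan says.** AUCτ is a secondary endpoint (Section 4.2). Section 14.3 defines it as "Area under the plasma concentration-time curve from time zero to 24 hours (dosing interval) at steady state". In Part 1 the steady-state profile is taken "on Cycle 3 Day 1 as follows: 0 (pre-dose), 0.5, 1, 1.5, 2, 3, 4, 6, 8 hr"; later samples are troughs. After the single Cycle 1 dose, by contrast, Table 7 also has samples at 24, 72 and 168 h.

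For Part 2, Table 8 schedules pre-dose samples, and only one visit adds a post-dose sample: "On cycle 1 day 15, samples will be obtained pre-dose and 6 hours post-dose (+/- 15 min". Section 14.5 nevertheless states: "Pharmacokinetic parameters of TRC253 will be determined using non-compartmental analysis and summarized by dose level/study part". For half-life and related parameters Section 14.3 requires that "at least 3 data points are used in the calculation". After the last Part 2 dose only two samples are scheduled: "The End of Treatment visit will be 7 days (± 2 days) after the last dose of TRC253", with Follow-Up 28 days after that.

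Three provisions bear on parameters that cannot be derived. Section 14.3 derives parameters after single and repeat dosing only where applicable. Section 14.1 says "patients will be removed from the estimation of certain PK parameters on an individual basis due to, for example, missing PK samples". Section 14.5 excludes patients whose concentrations are insufficient for parameter calculation, and it plans a population PK model with its own analysis plan.

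**The concern.** The endpoint covers 24 hours and the samples cover 8. The plan has rules for extrapolating to infinity, for minimum points, for fit, for values below quantification and for mistimed samples, but none for the last 16 hours of the steady-state interval. Two analysts could fill that stretch differently and report different AUCτ values from the same data.

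Part 2 looks worse. Two samples cannot locate tmax, and two washout samples fall short of the required three. Yet the tables are promised by study part, and Part 2 (up to 60 patients) will hold most of the data at 280 mg. Section 2.4 describes 2 Part 1 patients who started at 280 mg, 1 who escalated to it and 2 who were reduced to it: 2 + 1 + 2 = 5. If those tables could not be filled, exposure at the recommended dose might go unreported.

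**Working it through.** **Inputs.** Sampling times come from Tables 7 and 8 and parameter definitions from Section 14.3. Animal half-lives (Section 2.2.3) are "longer in the dog and monkey (58 and approximately 50 hours) than in the mouse and rat", where they are about 6 and 8 h. Repeat-dose tmax in rat and dog is generally 2 to 7 h. The text available for this review gives no human half-life, although Section 5.2 anticipates a long one. Human values below are therefore assumptions, shown over a range.

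**Step 1: how much is unsampled.** 24 − 8 = 16 h, and 16/24 = 67% of the interval.

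**Step 2: is the 24-hour value really missing?** For a one-compartment oral model at steady state, up to a constant,

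C(t) = ka/(ka − ke) × [e^(−ke·t)/(1 − e^(−24ke)) − e^(−ka·t)/(1 − e^(−24ka))], with ke = ln 2/half-life.

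This gives C(24) = C(0), so the pre-dose sample on Cycle 3 Day 1 supplies the 24-hour point once steady state is reached. The fraction reached after h hours is 1 − 2^(−h/half-life). Daily dosing runs 28 days (672 h) from Cycle 2 Day 1 to Cycle 3 Day 1. At a 100 h half-life that is 1 − 2^(−6.72) = 0.991, and it is higher for shorter half-lives.

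**Step 3: error in AUCτ.** Trapezoid to 8 h, then from 8 h to the pre-dose value placed at 24 h, without noise, for a single-dose tmax of 4 h:

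| Half-life (h) | Share of AUCτ by 8 h | Error, linear | Error, log-linear |
|---|---|---|---|
| 6 | 52.9% | +10.2% | −1.4% |
| 8 | 49.0% | +6.8% | −0.7% |
| 24 | 39.2% | +1.0% | −0.1% |
| 50 | 36.2% | +0.2% | 0.0% |
| 58 | 35.9% | +0.2% | 0.0% |
| 100 | 34.8% | 0.0% | 0.0% |

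For tmax from 2 to 7 h, the linear error at 50 to 58 h is +0.1% to +0.2%. At the rodent half-lives of 6 to 8 h it is +1.3% to +10.2% linear and −5.0% to −0.3% log-linear.

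**Step 4: add noise.** In 20,000 profiles per setting (half-life 30 to 100 h, ka 0.25 to 1 per h, 10% lognormal noise), the linear version has mean bias of about 1% or less and a standard deviation of about 5%. At most about 0.1% of profiles are more than 20% off.

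**Step 5: Part 2, parameter by parameter.**
- Cmin comes directly from the pre-dose samples, and the 6 h concentration is also available.
- tmax and a first-dose profile are not obtainable.
- Terminal half-life is not obtainable: the washout samples fall at about 7 and 7 + 28 = 35 days, two points against three.
- AUCτ and CL/F are not obtainable from sampling alone, but a two-sample trapezoid reusing the pre-dose value at 24 h has simulated mean bias of −4% to −1% (SD 7%). The planned population model can use the same samples.

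**Step 6: what depends on AUCτ.** Section 14 plans no formal hypothesis testing. The minimum efficacious dose in Section 5.1.1 is judged on mean trough against 335 ng/mL, and troughs are sampled. The QTcF endpoint uses Cmax and a concentration slope. The 280 mg dose has already been chosen.

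**The case for a change.** The strongest case is that another rule is conceivable and performs badly. In the same simulation, extrapolating the 4, 6 and 8 h log-slope to 24 h puts about 34–46% of profiles more than 20% from the true AUCτ. The r² criterion in Section 14.3 does not forbid this; failing it only labels the result an approximation.

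That figure mostly reflects an analysis nobody would report. Between 63% and 87% of the bad profiles have a rising slope from 4 to 8 h, which means a negative elimination rate constant. Only about 2–4% of all profiles have a declining slope, meet the 0.90 threshold and are still more than 20% off.

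It can also be argued that accumulation ratios inherit the gap, because Cycle 1 has a 24 h sample and Cycle 3 does not. That would be true of a ratio of 24-hour AUCs computed with no 24 h value. But the two cycles share identical times from pre-dose to 8 h, so a 0–8 h AUC ratio or a Cmax ratio needs no added rule, and Section 14.3 does not tie the accumulation index to the 24-hour AUC.

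Finally, the Part 2 samples were never scheduled, so provisions for missing data fit awkwardly. This stands in part: the by-study-part wording promises more than Table 8 can deliver, and the plan does not expressly assign Part 2 exposure to the population model. But the removal in Section 14.1 is from particular parameters, so patients keep their trough and 6 h data.

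**Conclusion.** The description of the text is right: there is no stated rule for 8 to 24 h, and Part 2 cannot yield tmax, terminal half-life or a first-dose profile non-compartmentally. No change is needed. A PK analyst will fill the Part 1 gap with the pre-dose value, at a cost of about 0.2% or less at half-lives of 50 to 58 h and about 1% mean bias or less with noise at 30 to 100 h. In Part 2, unsupported parameters drop out under existing wording, troughs and 6 h values are tabulated, and the planned population model can supply exposure.

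This rests on a one-compartment model, regular dosing around Cycle 3 Day 1, and a human half-life that is long but assumed. If it were as short as in rodents, the choice between linear and log-linear trapezoid would matter by up to about 10%. Even then it would affect a descriptive summary on which no decision in the plan depends.
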